
Incomplete Response/ Stable Disease (SD)	Persistence of one or more non-target lesion(s) or/and maintenance of tumor marker level above the normal limits
------------------------------------------	------------------------------------------------------------------------------------------------------------------

^a Although a clear progression of “non-target” lesions only is exceptional, the opinion of the treating physician should prevail in such circumstances, and the progression status should be confirmed at a later time by the Investigator.

Evaluation of Best Overall Response

The best overall response is the best response recorded from the start of the treatment Sunitinib until disease progression/recurrence (taking as reference for PD the smallest measurements recorded since the treatment started). In general, the subject's best response assignment will depend on the achievement of the measurement criteria.

Table 6 Evaluation of Best Overall Response

Target Lesions	Non-Target Lesions	New Lesion	Overall response
CR	CR	No	CR
CR	Incomplete response/SD	No	PR
PR	Non-PD	No	PR
SD	Non-PD	No	SD
PD	Any	Yes or No	PD
Any	PD	Yes or No	PD
Any	Any	Yes	PD

Subjects with a global deterioration of health status requiring discontinuation of treatment without objective evidence of disease progression at that time should be classified as having “symptomatic deterioration.” Every effort should be made to document the objective progression even after discontinuation of treatment.

Note: For intermediate-risk patients included in the trial according to protocol versions before version Final 4.0, the first imaging assessment after nephrectomy will be used as baseline for evaluation of best overall response, irrespective of whether or not the imaging assessment coincided with sunitinib treatment start. Further details will be provided in the SAP.

Definitions for Response Evaluation

a) Confirmation of Response

To be assigned a status of complete or partial response, changes in tumor measurements do not need to be confirmed by repeat assessments after the criteria for response are first met.

b) Response rate

To be evaluated as the highest observed score of response during the study after randomisation in the ordinal categories of CR, PR, PD, SD and “Not evaluable”. The response rate will be evaluated according to the Schedule of Study Events, *Section 7.2.1*.

c) Objective response

Is defined as the proportion of patients with CR and PR.

d) Disease control rate (DCR)

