12.1.6 Secondary Efficacy Analyses

Secondary efficacy endpoints will be presented descriptively by stratum (High-/Intermediate-risk mRCC patients) as stated explicitly for each endpoint below. Further analyses may be defined in the SAP, if appropriate. All secondary endpoints will be evaluated using the FAS. In addition, the PPS will be used.

PFS from start of sunitinib in intermediate and high-risk mRCC patients

The PFS analysis will be based on the subgroup of patients from FAS that actually had been exposed to at least one dose of sunitinib. PFS will be evaluated using similar survival statistics as described for the analysis of the primary endpoint.

Note: For intermediate-risk patients included in the trial according to protocol versions before version Final 4.0, sunitinib treatment did not have to be initiated at a fixed time point. For these patients, the first imaging assessment after nephrectomy will be used as baseline for evaluation of PFS, irrespective of whether or not the imaging assessment coincided with sunitinib treatment start. Further details will be provided in the SAP.

All other secondary endpoints defined as a time-to-event endpoint will be analyzed using the same statistical approach.

Response rate from Sunitinib Start Visit

Evaluation of response rate, based on CT and according to the RECIST 1.1 guideline, from Sunitinib Start Visit will be based on the subpopulation from FAS who have been exposed to at least one dose of sunitinib. Number of patients with CR, PR, PD, and SD after start of sunitinib will be summarized as described in *Section 12.1.4* for categorical data, using the underlying ordinal scale.

ORR including DCR will be summarized descriptively. Waterfall charts will be used to display the response distribution, details for this will be provided in the SAP. Between group comparison of the proportions will be done using Cochran Mantel Haenzel test including stratum on high-risk and intermediate-risk groups as a fixed factor.

Note: For intermediate-risk patients included in the trial according to protocol versions before version Final 4.0, the first imaging assessment after nephrectomy will be used as baseline for evaluation of ORR, irrespective of whether or not the imaging assessment coincided with sunitinib treatment start. Further details will be provided in the SAP.

Number of infiltrating CD8+ T-cells

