- Sunitinib Start Visit (Sun-Start), five (5) to eight (8) weeks after Nephrectomy
- Sunitinib Follow-up Visits (SFU[6W] and SFU[12W]), every 6 weeks for 12 weeks or until locally CT-verified PD whichever occurs first
- Sunitinib Follow-up Visits (SFU[24W], SFU[36W], SFU[48W], and SFU[60W]), every 12 weeks until End-of study or until locally CT-verified PD whichever occurs first
- End-of-Study Visit (End-of-Study)

The above described visits are applicable to all randomized subjects after and including protocol version 4.0. Subjects entering the trial corresponding to protocol versions prior to this, were included following a visit pattern that was different for high and intermediate risk patients. Following this design intermediate risk subjects would only start sunitinib treatment after confirmed PD.

At the two (2) Vaccination Visits, the patients are be administered Intuvax (10 x10⁶ DCs) intratumorally in the viable part of their primary tumor. Vaccine from the same batch (i.e. the same donor) is be used at both occasions. The patient stay at the clinic at least four (4) hours after vaccination. Nephrectomy is done at least 3 days after the second vaccination and maximum 63 days after Screening. Sunitinib treatment is initiated five (5) to eight (8) weeks after nephrectomy, administered dose is in accordance with the SmPC/USPI.

All patients are encouraged to contact the clinic in between study visits if they experience adverse events (AEs) or have any concerns. If follow-up of any symptoms is needed between the planned visits, the patient are scheduled for a visit as soon as possible and applicable assessments are performed.

A diagram of the study design is provided in Figure 1, and a flow chart what all assessments to be conducted per visit are provided in Tables 1 and 2.

Post-study survival data (either patient alive or date of death) will be collected.

[figure not shown]

Figure 1 Overall Study Design

Table 1 Study Flow Chart

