5 DATA SETS TO BE ANALYSED

The following analysis sets will be used for the statistical analysis and presentation of data:

- **The safety set:** All randomized patients with at least one safety assessment at Screening.
- **The full analysis set (FAS):** All randomized patients being evaluable for any efficacy endpoint
- **The per protocol set (PPS):** All patients randomized to Intuvax who had both doses of Intuvax administered or patient randomized to sunitinib alone, both having the nephrectomy and who continued the trial without any major protocol violations that could interfere with the objectives of this study. The criteria for PPS, regarding which protocol deviations that warrant exclusions will be determined by the following criteria.
 - Violations to inclusion, exclusion and withdrawal criteria
 - Deviations relating to primary and secondary objectives/endpoints
 - Study medication (Intuvax or Sunitinib): That was not stored and/or prepared and/or administered as defined in the protocol
 - Administration of prohibited concomitant medication
 - Availability of required data

The exact criteria that warrant exclusion from PPS will be documented in relation to review of the reported PDs. The patients excluded with reference to the PD leading to exclusion will be listed and signed off in in the *Pre-Analysis Review Form* before DBL.

The FAS is considered as the primary analysis population, and will be used for all primary and secondary efficacy analyses. The primary efficacy analysis will be repeated using the PPS. Any significant discrepancy between the results from the FAS and the PPS will be analysed and discussed.

Secondary efficacy endpoints defined as to be analyzed after start of sunitinib will be based on the subset of subjects in FAS having at least one dose of sunitinib (or as described for PFS, when subjects were included according protocol versions prior to version 4.0).

Baseline and safety will be presented using the safety set.

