6.3 Hypotheses and Statistical Methods

6.3.1 Definitions

Baseline The date of randomization is defined as baseline for OS and 18-month survival rate.

The centrally assessed CT performed at the Sunitinib Start Visit is defined as CT baseline for evaluation of PFS, response rate and TTP after start of sunitinib in intermediate- and high-risk patients

The Screening Visit is defined as baseline for all other assessments than those listed above.

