6.3.6 Secondary Efficacy Analyses

PFS from start of sunitinib according to RECIST 1.1

PFS from start of sunitinib treatment will be derived as date whichever occurred first of any cause of death or date for first tumor progression (which is date for centrally assessed CT performed, according to RECIST 1.1) minus date for start of sunitinib treatment plus 1 day.

For the analysis of PFS only deaths occurring before end-of-trial will be accounted for in the analysis.

Analysis of PFS will be evaluated the following way:

Survival functions will be displayed graphically using Kaplan-Meier plots, and life table statistics will be produced including summaries of number of events and censored observations. Estimates of cumulative 25%, 50% (median) and 75% percentiles of survival with corresponding 95% confidence intervals will be calculated.

Comparison between Intuvax+sunitinib, vs. sunitinib alone will be done using a stratified log-rank test (controlling for strata intermediate/high risk), separate analyses will also be done by strata.

With protocol versions before version 4.0, intermediate risk patients did not have to initiate treatment with sunitinib at a fixed time point according to the visit schedule. Consequently some patients were never started on sunitinib, and in some cases sunitinib treatment was initiated at a later time point. The sunitinib start date constitutes the baseline time point for PFS according to protocol version 4.0 and after. In the analyses, patients who either had a delay or never started sunitinib will be included under the assumption that sunitinib treatment would have been initiated according to the final design, the date of the visit following the nephrectomy visit will be used as baseline.

Another issue that will be considered in the analysis is that some patients may have been discontinued based on general clinical disease progression as evaluated by investigator from symptoms/signs of disease, rather than based on a PD according to RECIST 1.1. For the analysis such cases will be handled strictly based on the RECIST 1.1 evaluation, thus if a patient is withdrawn without a CT confirmed PD the subject will be censored at last CT

Analyses will be based on FAS and repeated for separately by strata..

Proportion of Objective Response Rate (ORR) and Disease Control Rate (DCR) from start of sunitinib

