Proportion of ORR from start of sunitinib treatment will be derived as the proportion of patients with the individual's best overall response scored as "CR" or "PR" (using RECIST 1.1) across all time points from first visit six (6) weeks after sunitinib treatment, to end-of-study visit. Similarly, DCR will be derived as proportion of patients with best overall response scored as "CR", "PR" or "SD".

ORR and DCR will be summarised and comparison of treatment groups will be made using the Cochran Mantel-Haenzel test, adjusting for strata.

Duration of response will be derived only for patients meeting the ORR definition CR or PR, at least once, as the date of the first occurrence of PD or death minus the date at which the CR or PR was first observed, plus 1 day. Patients without an occurrence of a PD or death after CR or PR will contribute with the time up till last tumor assessment. Data will be summarised descriptively.

Duration of clinical benefit will be derived only for patients meeting the DCR definition CR, PR or SD at least once, as the date of the first occurrence of PD or death minus the date at which the CR, PR or SD was first observed, plus 1 day. Patients without an occurrence of a PD or death after CR, PR or SD will contribute with the time up till last tumor assessment. Data will be summarised descriptively.

The duration of stable disease is calculated for only those patients who exhibited a best response of stable disease response and will be calculated as the date for the first SD

response to the date of the first observed progression of disease or death before end of trial, if the death was due to disease progression (whichever comes first) plus 1 day. Data will be summarised descriptively.

Response rate from Sunitinib Start Visit

Evaluation of response rate, based on CT and according to the RECIST 1.1 guideline, from Sunitinib Start Visit will be based on the subpopulation from FAS who have been exposed to at least one dose of sunitinib. Number of patients with CR, PR, PD, and SD after start of sunitinib will be summarized using the underlying ordinal scale.

Waterfall charts will be used to display the percent change in target lesion tumour dimension vs best overall response and Two types of Swimmer plots will be created, one with bars showing time from randomization and one from sunitinib start. In these events for progressive disease, end of trial and vital status will be indicated.

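### For intermediate-risk patients enrolled before protocol 4.0, the documents give conflicting populations, baselines and scan windows for response rate, ORR and DCR

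*SAP*

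**What the plan says.** Call intermediate-risk patients enrolled under protocol versions before 4.0 the early intermediate-risk patients. SAP 4.1 describes their design: "intermediate risk subjects would only start sunitinib treatment after confirmed PD". SAP 6.3.6 reports the result: "Consequently some patients were never started on sunitinib", and others started late. Three sets of rules then apply.

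- **Population.** Under its response-rate heading, SAP 6.3.6 says the evaluation "will be based on the subpopulation from FAS who have been exposed to at least one dose of sunitinib". Protocol 12.1.6 has the same restriction, under a heading that also covers ORR and DCR. SAP section 5 restricts secondary endpoints read after sunitinib start in the same way but adds an alternative: "or as described for PFS, when subjects were included according protocol versions prior to version 4.0". The PFS text it points to says that "patients who either had a delay or never started sunitinib will be included under the assumption that sunitinib treatment would have been initiated" on the final schedule. The ORR/DCR paragraph of SAP 6.3.6 names no population.
- **Baseline.** Protocol 12.1.6 says that for these patients "the first imaging assessment after nephrectomy will be used as baseline for evaluation of ORR", and leaves details to the SAP. SAP 6.3.1 says: "The centrally assessed CT performed at the Sunitinib Start Visit is defined as CT baseline for evaluation of PFS, response rate and TTP". It has no variant for early patients; SAP 6.3.6 gives one under PFS only.
- **Scoring window.** Protocol 10.2.2.2 says: "The best overall response is the best response recorded from the start of the treatment Sunitinib until disease progression/recurrence". The ORR/DCR paragraph of SAP 6.3.6 takes the best score over visits from six weeks after sunitinib to the end-of-study visit, and does not say whether scans after PD count.

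ORR and DCR are compared by a Cochran-Mantel-Haenszel test stratified by risk group. Protocol version is not a factor.

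**The concern.** Followed literally, the exposed-only rule admits an early intermediate-risk patient only if the disease has progressed since nephrectomy. A patient who stayed progression-free off sunitinib is left out. Everywhere else in the trial sunitinib is scheduled five to eight weeks after nephrectomy, so exposure does not depend on progression in that way.

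Under the alternative in SAP section 5 these patients are in, but the window and baseline that the SAP gives for response do not suit them. A programmer must then choose population, baseline and window. SAP 6.2 acknowledges that ongoing data review in this open-label trial is not blind, so the choice could be made with outcomes visible. At stake is whether ORR and DCR describe response from the start of sunitinib, and whether the arms are compared on a set whose membership could itself depend on treatment.

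**Working it through.** The documents give no expected ORR or DCR, no count of early intermediate-risk patients and no power calculation, so there is no planned figure to reproduce. The check has three parts.

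**1. The rules applied to the two kinds of early patient**

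| Rule | Started after PD | Never started |
|---|---|---|
| Response-rate text (SAP 6.3.6, Protocol 12.1.6) | in | out |
| SAP 5 with the PFS rule | in | in |
| Protocol baseline | first post-nephrectomy scan, before the PD | first post-nephrectomy scan |
| SAP 6.3.1 baseline | Sunitinib Start CT | not defined |
| SAP ORR/DCR window | opens after the PD | no start date |
| Protocol window | from sunitinib start to progression | no start date |

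**2. The PR threshold with the post-nephrectomy baseline**

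Protocol Table 4 requires a sum of diameters at most 0.70 of baseline for PR and, for PD by target lesions, at least 1.20 of the smallest sum. Take the baseline as the smallest sum, and 20% growth before sunitinib. The shrinkage needed from the size at sunitinib start is 1 − 0.70/1.20 = 41.7%, against 30% for a patient whose baseline is the Sunitinib Start CT. If scoring runs from the post-nephrectomy scan and stops at first PD, the scans on sunitinib come after the stop and cannot contribute.

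**3. Illustrative size**

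Assumptions, none of them in the documents:

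- Final-design ORR 35% and DCR 75%.
- f = share of patients who are early intermediate-risk, 5–30%.
- q = share of those who progress and start sunitinib, 40–80%.
- s = share of those started who are scored SD, 0–50%. None is scored CR or PR.
- Never-starters are scored SD.

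Formulas:

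- Exposed-only ORR = (1−f)·0.35 / [1−f(1−q)]
- Exposed-only DCR = [(1−f)·0.75 + f·q·s] / [1−f(1−q)]
- Never-starters included: ORR = (1−f)·0.35; DCR = (1−f)·0.75 + f·[(1−q) + q·s]

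At f = 20%, q = 60%, s = 25%:

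- Exposed-only: ORR 0.280/0.92 = 30.4%; DCR (0.600 + 0.030)/0.92 = 68.5%.
- Never-starters included: ORR 28.0%; DCR 0.600 + 0.110 = 71.0%.

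| f | Exposed-only ORR | Exposed-only DCR | Never-starters dropped, of 90 |
|---|---|---|---|
| 5% | 33.6–34.3% | 72.0–74.5% | 0.9–2.7 |
| 10% | 32.1–33.5% | 68.9–73.9% | 1.8–5.4 |
| 20% | 29.2–31.8% | 62.5–72.7% | 3.6–10.8 |
| 30% | 26.1–29.9% | 55.9–71.3% | 5.4–16.2 |

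**Between arms**, with no effect on response to sunitinib: if q is equal in both arms, the exposed-only difference is zero. If q is 40% with vaccine and 80% without, it is 1.4–3.8 points for ORR and 1.0–8.2 points for DCR (f = 10–30%). The upper end is f = 30%, s = 0: DCR 0.525/0.82 − 0.525/0.94 = 64.0% − 55.9%, or 8.2 points before rounding. Including never-starters does not remove the DCR difference: it becomes 2–12 points over the same range.

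**The case against.** The best defence is that SAP section 5 already settles the population. It covers secondary endpoints read after sunitinib start, makes an exception for early patients, and the SAP's ORR/DCR paragraph has no exposed-only sentence of its own. On that reading the selection does not occur for ORR and DCR. This is a fair reading and limits the claim. It does not settle the matter: the SAP's own response-rate text and Protocol 12.1.6 state the restriction without the exception. Nor does section 5 supply a response baseline or window.

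Three stronger readings are tempting, and the documents do not support them.

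- *The patients left out are those with the best outcomes.* SAP 6.3.6 gives no reason why patients never started. Early death or withdrawal would also leave a patient unexposed.
- *Every early patient kept is a forced non-responder.* That needs the post-nephrectomy baseline and a stop at first PD, both from the protocol. On the SAP's rules alone (Sunitinib Start CT, all visits to end of study) a response on sunitinib can count. Even with the earlier baseline, PR remains reachable if post-PD scans are scored. SD before progression would count toward DCR. Nor do the documents say who confirmed the PD that triggered sunitinib, whereas endpoints use central reads (Protocol 10.4.3).
- *The comparison between arms is biased.* That requires pre-sunitinib progression to differ by arm.

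The endpoints are secondary and all testing is exploratory. SAP 6.2 allows minor clarifications before database lock. Both points lower the consequence, but choosing between populations and baselines is more than a minor clarification.

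**Conclusion.** The concern holds as a conflict of rules for one subgroup. The response-rate text selects early intermediate-risk patients on confirmed PD, while section 5 with the PFS rule does not. The SAP's response baseline departs from the protocol's for these patients. Its ORR/DCR window is undefined for never-starters and follows PD for delayed starters. The only firm size is the threshold: about 42% shrinkage instead of 30%, given the post-nephrectomy baseline as smallest sum and 20% target-lesion growth before sunitinib.

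A reader might infer that reported ORR and DCR will be distorted by a known amount. They cannot be sized: the rates above rest on assumed values of f, q and s and on assumed final-design rates. Direction also depends on the comparison. In the worked case exposed-only rates fall below the assumed final-design rates, yet exposed-only ORR is higher, and DCR lower, than with never-starters included. The OS and 18-month survival analyses are unaffected, since they run from randomization in the FAS.

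**What to change.** In SAP 5, 6.3.1 and 6.3.6, state one population, one baseline and one scoring window for early intermediate-risk patients. Apply them to response rate, ORR, DCR and the waterfall charts. To agree with the PFS rule, include these patients whether or not they received sunitinib, take the first post-nephrectomy CT as baseline, and say from which scan scoring runs and whether it stops at first centrally read PD. The SAP anchors PFS on the visit after nephrectomy and the protocol on the first imaging after it; one anchor should serve all these endpoints.

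Including never-starters is not enough: in the worked case it moves DCR toward the assumed final-design value (68.5% to 71.0%) but ORR further away (30.4% to 28.0%). So repeat ORR and DCR without early intermediate-risk patients, and label that the analysis which matches response from the start of sunitinib. Report the number of early intermediate-risk patients, and how many started sunitinib, by arm.

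The cost is SAP wording before database lock, one extra set of tables, and a smaller set with less precision in the repeat analysis.
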